### **Safety Assessments**

Safety will be evaluated with Fisher's exact tests, by comparing the following assessments between the MMFS-202-302 and Placebo groups: adverse events, laboratory test results, vital signs, body weight, and subjective remarks. The safety population will include all subjects who had at least one exposure to a study compound, and who had any subsequent encounter with the study staff.

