Alpha will be set at 0.05 for all analyses. The individual scores for each of the 6 other neuropsychological MCB subscales, and supplementary cognitive tests (ACT, WCST, FAS), as well as the CGI-C measure of functional change will be evaluated to provide supporting information for primary and secondary measures.

Assumptions for the power analysis included random assignment into one group receiving placebo and one MMFS-202-302. The MCB, as the primary instrument will be collected at baseline and at end point (9 weeks). Using univariate ANCOVA with baseline score as covariate, the time average difference in the response variable will be compared between groups to detect treatment difference. Based on Javitt et al, 2012, we assume the mean baseline working memory score will be 36.4, SD 11.7 for both groups. We assume the placebo group will show no improvement with an SD of change of 6.5, while the treatment group will improve a mean of 5 points with the same SD of change, a medium effect. We assume the correlation coefficient of repeated observation to be 0.5 and the covariance structure to be compound symmetry. The power calculation was conducted with alpha level of 0.05. Full results are available upon request. With a two-sided test, the analysis reveals that 28 subjects per group are required assuming 5 points of improvement of the treatment group compared to the placebo for the desired power of 80% with alpha level of 0.05. We plan to recruit 30 per group to account for drop outs. Thus, allowing for attrition up to 20%, this sample size will provide 74-83% power to detect the hypothesized medium treatment effect.

We will assess MMFS-202-302 effects on negative and positive symptoms as additional endpoints, as measured by the BNSS and PANSS. Further, we will analyze the effect on drug tolerability as determined by the following: body weight, body mass index (BMI), waist circumference, and movement rating scales.

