### **9.1.9 Vital Signs**

Arterial systolic and diastolic blood pressure and radial artery pulse rate will be measured while the patient is seated at the scheduled visits designated in the Schedule of Events in Appendix 1.

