#### **9.1.9.1 Height and Body Weight**

Height will be measured at the screening visit. Patients will be measured without shoes. Body weight will be recorded at screening, baseline and every visit through the 9-week treatment phase.

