#### **9.1.14 Laboratory Test Assessments**

Northwestern Medicine Laboratory will be used for analysis of fasting lab assessments required during the study. Blood will be drawn from each patient at the screening visit, and at end of study as noted in the study Schedule of Events in Appendix 1. The fasting tests will include: Hematology and chemistry panels; pregnancy (women of childbearing potential only), serum creatinine, and urine drug screen (UDS).

Note: At screening and throughout study participation, a positive UDS or blood alcohol screen is not necessarily exclusionary and/or may not require a subject be withdrawn from the study. This decision will be per the discretion of the principal investigator.

A blood sample will be collected and analyzed for plasma Mg2+, Red blood cell Mg2+ (RBC-Mg) and total RBC cell count.

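### Fisher's exact test is assigned to laboratory results, vital signs and body weight, which are mainly continuous, with no categories defined and no continuous analysis specified

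*Combined protocol and SAP*

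**What the plan says.** The Safety Assessments paragraph of section 3.0 names one method: "Safety will be evaluated with Fisher's exact tests, by comparing the following assessments between the MMFS-202-302 and Placebo groups". It applies that method to five items: "adverse events, laboratory test results, vital signs, body weight, and subjective remarks".

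Section 8.1 returns to body weight in a tolerability analysis covering "body weight, body mass index (BMI), waist circumference, and movement rating scales". It gives no test, model or summary statistic for them.

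The procedure sections show what kind of data these are.
- Vital signs (9.1.9): "Arterial systolic and diastolic blood pressure and radial artery pulse rate will be measured while the patient is seated".
- Weight (9.1.9.1): "Body weight will be recorded at screening, baseline and every visit through the 9-week treatment phase".
- Laboratory tests (9.1.14): "Hematology and chemistry panels; pregnancy (women of childbearing potential only), serum creatinine, and urine drug screen (UDS"). This is a mixture: the panels and creatinine are mainly continuous, while the pregnancy test and drug screen are binary. A separate paragraph of the same section adds plasma and red-cell magnesium.

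Appendix 1 schedules vital signs, safety laboratory tests and blood magnesium both before dosing and at the end of study. On significance level, section 8.1 says "Alpha will be set at 0.05 for all analyses".

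**The concern.** Fisher's exact test compares counts in categories. To apply it to blood pressure, creatinine or weight, someone must first decide what counts as an event, and the plan leaves that undecided. Elsewhere it does define its categories: a T-score gain of at least 5 for responders, and T-scores of 50, 45 and 40 for the subgroups. For efficacy it also specifies ANCOVA with the baseline value as covariate. The continuous safety measures get neither. As written, their analysis cannot be run without a later choice, possibly made after the data have been seen.

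The natural reading is a count of out-of-range values. That ignores where each patient started and how far the value moved. The protocol lists hypotension and cardiac arrhythmia among the effects of excess magnesium and excludes kidney dysfunction because of magnesium clearance. Moderate shifts in creatinine or blood pressure are therefore among the things a reader would want estimated, and a comparison of counts with 30 per arm estimates them poorly.

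**Working it through.** **The plan's own figure.** The only power statement is for the primary efficacy endpoint: difference 5, SD of change 6.5, two-sided 0.05. The normal approximation gives n = 2 × (1.960 + 0.842)² × (6.5/5)² = 2 × 7.85 × 1.69 = 26.5, so 27 per group. The t-based calculation gives 27.5, so 28, as stated. Its power is 74.2% at 24 per group (30 less 20%) and 83.4% at 30, matching the stated 74-83%. This concerns efficacy only. No power, effect size, SD or cut-off is given for any safety measure.

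**Inputs for the safety check.** From the plan: 30 per arm, 1:1 allocation, alpha 0.05. Assumed, because the plan is silent: two-sided testing; change from baseline normally distributed with equal SD; every treated patient shifted by the same d = 0.5, 0.75 or 1.0 SD; a cut-off exceeded by a share p of placebo patients.

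**Comparison of means.** The noncentrality is d × √(30/2), with 58 degrees of freedom and critical value 2.002. For d = 0.75 it is 2.905, giving 81.5% power. For d = 0.5 it is 1.936, giving 47.8%.

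**Fisher's exact test.** The treated share beyond the cut-off is 1 − Φ(z − d), where z is the normal quantile exceeded by a share p. For p = 10% and d = 0.75 this is 1 − Φ(1.282 − 0.75) = 29.8%. For p = 5% it is 1 − Φ(1.645 − 0.75) = 18.5%. Power is the summed probability of all pairs of binomial counts (0 to 30 in each arm) with Fisher p ≤ 0.05.

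| Shift (SD) | Means | Fisher, p = 5% | p = 10% | p = 20% | p = 50% |
|---|---|---|---|---|---|
| 0.5 | 47.8% | 4.9% | 13.0% | 21.2% | 23.7% |
| 0.75 | 81.5% | 19.1% | 36.3% | 48.5% | 49.7% |
| 1.0 | 96.8% | 47.5% | 67.3% | 77.0% | 74.8% |

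Between p = 20% and p = 50%, Fisher power peaks slightly higher: about 25% at 0.5 SD, 53% at 0.75 SD and 80% at 1.0 SD.

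**Share of power lost at 0.75 SD.** 1 − 19.1/81.5 = 77% (p = 5%); 1 − 36.3/81.5 = 55% (10%); 1 − 48.5/81.5 = 40% (20%); 1 − 49.7/81.5 = 39% (50%). At 0.5 SD the losses are 90%, 73%, 56% and 50%.

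**A concrete count.** With no abnormal values among 30 placebo patients, k of 30 on drug gives p = 2 × C(30,k)/C(60,k). For k = 5 this is 0.052 and for k = 6 it is 0.024. Six of 30 treated patients (20%) must be abnormal before the test reaches 0.05.

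**The case against.** The strongest defence is that counting abnormal values fits the protocol's own framework. Its adverse event definition includes abnormal laboratory findings, and Fisher's test is valid for such counts. The uniform-shift model also favours means. The protocol describes hypermagnesemia as rare, which suggests a few strongly affected patients. If 30% of treated patients shift by 3 SD (an assumption), the t-test has 70% power and Fisher 63-68% at cut-offs flagging 1-5% of placebo. If only 10% shift, by 3 to 8 SD, the t-test has 15-28% and Fisher 3-8%. Neither serves well then, and the cause is the sample of 60. This stands as a reason to keep the abnormality counts alongside the means. It does not supply the missing categories or justify having no continuous analysis.

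Four stronger readings are tempting, and the documents do not support them.
- *Fisher's test governs all safety data.* The list has five items. The movement scales, C-SSRS and ECG are not on it, some laboratory items are binary, and section 8.1 leaves the method for weight, BMI and waist open.
- *Most of the power is lost.* That holds at cut-offs few placebo patients exceed, or for small shifts. At 0.75 SD with cut-offs flagging 20-50% of placebo, Fisher keeps more than half of the power.
- *Magnesium is certainly tested this way.* Appendix 1 schedules blood magnesium separately from the safety laboratory tests, so its method is unclear.
- *A non-significant result will be taken as reassurance.* No section says so.

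**Conclusion.** The point holds as a specific defect in the safety analysis. A categorical test is assigned to mainly continuous measures, no categories are defined, and no other method for laboratory values or vital signs appears anywhere. Weight appears twice, once with Fisher's test and once with no method.

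At 30 per arm and an assumed uniform shift of 0.75 SD, power falls from 81.5% to between 19% and 53% for cut-offs flagging 5% to 50% of placebo. At 0.5 SD it falls from 48% to between 5% and 25%. The direction is the same at every uniform shift and cut-off tested, but the size depends on a shift and a cut-off that the plan does not give. The comparison uses an unadjusted test of change. The primary endpoint and the sample size are unaffected. The change should be made, but the trial's main conclusion does not depend on it.

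**What to change.** - Limit Fisher's exact test to adverse event incidence, binary laboratory items and counts of abnormal values whose limits are written down before unblinding.
- For continuous laboratory values, vital signs, weight, BMI and waist circumference, add ANCOVA of change from baseline to week 9 with the baseline value as covariate. Report the adjusted mean difference and 95% confidence interval as descriptive safety estimates. For safety laboratory tests the pre-dose value is the screening sample.
- State explicitly that plasma and red-cell magnesium are included.
- Reconcile section 3.0 with section 8.1 so that weight has one stated method, and name a method for the movement scales.

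All the measurements are already scheduled, so the cost is analysis-plan wording and a few tables. The downside is more unadjusted safety comparisons, and some will cross 0.05 by chance. The report should therefore rest on estimates and intervals rather than p-values, with the abnormality counts shown beside them.

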## 5.0 TREATMENT PLAN

### 5.1 Study Design

#### Design of Clinical Trial

After providing written informed consent and completing baseline assessments, patients with schizophrenia or schizoaffective disorder will be randomized to placebo or MMFS-202-302. We will make every effort to enroll subjects who have had a recent fMRI assessment as part of the Northwestern University Psychiatric Clinical Research Program. This would provide valuable pre-dose information regarding any structural abnormality. No patients with tardive dyskinesia will be admitted because of the evidence for its deleterious effect on cognition.

Patients will be recruited primarily from three mental health clinics in the Chicago area, at which the principal investigator been successfully recruiting for the last 28 months: the Stone Mental Health Center which is a part of the Northwestern Medicine system, Community Counseling Centers of Chicago (C4), and Clayton House, a residential treatment center. Other mental health facilities in the area will also be referral sources. We expect to recruit 4-5 patients per month for this study without difficulty. We expect the recruitment to be complete within 12 months or less after approval by the Northwestern University Institutional Review Board and study initiation.

All patients who are screened must provide written informed consent. Our lab has trained and certified coordinators and research assistants who will be assigned to this study as their primary responsibility. We have used the MATRICS cognitive battery in many studies over the last five years. Because of our 20- year interest in cognitive impairment in schizophrenia, there are a few other cognitive tests we collect on all of our research patients. These include a measure of phonemic verbal fluency (FAS), the Brown- Peterson Auditory Consonant Trigrams test of working memory (ACT), and the Wisconsin Card Sorting Test (WCST). We have experienced no difficulty in administering the MATRICS battery and this group of tests, which takes another 30 minutes to our patients.

We propose to study a total of 60 randomized participants, 30 receiving MMFS-202-302 and 30 randomized to placebo.

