### **13.0 RISKS AND DISCOMFORTS**

All efforts are made to minimize risks to subjects. Consistent with good clinical practice, safety will be monitored by the Principal Investigator, and will reflect the oversight of co-investigator study clinicians. Adverse events will be recorded and reported according to institutional policies. Risks of the study agent have been incorporated into the exclusionary criteria for this proposal.

Study Agent – L-TAMS: L-TAMS is considered a dietary supplement that the manufacturer has self-certified as fulfilling the FDA criteria for agents that are Generally Regarded as Safe. There are few risks to taking L-TAMS orally. Magnesium is known to cause gastrointestinal discomfort, nausea, vomiting, or diarrhea. Although occurrences are rare, very large amounts of magnesium might cause hypermagnesemia with symptoms including thirst, hypotension, drowsiness, confusion, loss of tendon reflexes, muscle weakness, respiratory depression, cardiac arrhythmias, coma, cardiac arrest, and death. There have been only two reports of death from hypermagnesemia (Therapeutic Research Faculty (2014). *Natural Medicines Comprehensive Database* Retrieved May 30, 2014, from <http://naturaldatabase.therapeuticresearch.com/nd/Search.aspx?s=ND&cs=NDPTL~CP&pt=103&sh=7&id=89669&ft=4#reactions>).

MRI risks are minimal for subjects who are thoroughly screened and deemed safe for scanning. These include feelings of claustrophobic fear while being scanned, and minor physical discomfort because of remaining still throughout the scanning procedure.

EEG risks include the participant finding the tasks boring, tiring, and/or frustrating. If this happens, research staff will allow the participant to rest and then attempt continue. Participants might find the EEG cap to be uncomfortable. If this occurs, research staff will attempt to adjust the EEG cap so that it is more comfortable.

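### Adverse events are compared between arms only by Fisher's exact test, with no risk difference or confidence interval planned, so the analysis will not show how large a harm the data leave open

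*Combined protocol and SAP*

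**What the plan says.** Section 3.0, Safety Assessments, gives the between-arm method: "Safety will be evaluated with Fisher's exact tests, by comparing the following assessments between the MMFS-202-302 and Placebo groups". Adverse events head the list of assessments; laboratory results, vital signs, body weight and subjective remarks follow. The analysis set is defined there too: "The safety population will include all subjects who had at least one exposure to a study compound", with the further condition of a later contact with study staff.

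Section 8.1 fixes the significance level: "Alpha will be set at 0.05 for all analyses". No separate level is given for safety, and the sidedness of the Fisher test is not stated. The planned size is in section 5.1: "We propose to study a total of 60 randomized participants, 30 receiving MMFS-202-302 and 30 randomized to placebo".

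No section plans a risk difference, relative risk, confidence interval or upper bound for adverse events, and none gives power for safety. Section 8.1 adds a tolerability analysis, but it covers weight, BMI, waist circumference and movement scales, and names no method. Sections 9.1.11 and 11.4 to 11.7 describe how individual events are graded, attributed, followed up and reported. Those steps do not estimate a difference between arms.

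**The concern.** The protocol expects specific harms. Section 13.0 says: "Magnesium is known to cause gastrointestinal discomfort, nausea, vomiting, or diarrhea". Section 11.0 adds drowsiness, dizziness and headache on first use. The natural question for each is how much more often it occurs on drug than on placebo, and how large an excess the trial cannot rule out. A p-value answers neither.

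At this sample size most moderate excesses will come out non-significant. If the report gives only the test result, the reader cannot tell an absence of harm from an absence of information. Fixing the estimate and interval in advance also removes the freedom to choose how the result is worded once it is known.

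**Working it through.** **Inputs.** From the documents: 30 per arm (section 5.1); alpha 0.05 (section 8.1); a 5-point difference with SD of change 6.5, and up to 20% attrition (section 8.1). Assumptions: a two-sided Fisher test (two-sidedness is stated only for the efficacy sample size) and the event rates, since the documents give none.

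**The plan's own figures first.** The only power figures are for efficacy: "With a two-sided test, the analysis reveals that 28 subjects per group are required", and "allowing for attrition up to 20%, this sample size will provide 74-83% power to detect the hypothesized medium treatment effect". Take a two-sample t-test on change with noncentrality 5 / (6.5 × √(2/n)):
- n = 28: 5 / 1.737 = 2.88, power 80.7% (27 per arm gives 79.2%)
- n = 30: 5 / 1.678 = 2.98, power 83.4%
- n = 24 (30 × 0.8): 5 / 1.876 = 2.66, power 74.2%

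Both stated figures reproduce. There is no corresponding figure for safety.

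**Fisher test on adverse events.** Let X be the number of patients with the event on drug and Y the number on placebo, with X ~ Bin(30, p1) and Y ~ Bin(30, p0). Power is the sum of P(X = x) × P(Y = y) over all 31 × 31 tables with Fisher p ≤ 0.05. The share of trials that is non-significant is one minus this.

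| Placebo vs drug (assumed) | Non-significant, two-sided |
|---|---|
| 10% vs 20% | 90% |
| 10% vs 30% | 63% (power 37.2%) |
| 10% vs 40% | 29% |
| 5% vs 15% | 91% |
| 5% vs 20% | 76% |
| 5% vs 25% | 56% |
| 20% vs 40% | 70% |
| 0% vs 10% | 93% |

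For 10% vs 30%:
- a one-sided test at 0.05 is non-significant in 51% of trials
- a one-sided test at 0.025 is non-significant in 63%
- with 24 per arm, two-sided, the share is 69%. This is pessimistic, because the safety population keeps dropouts who had any later contact.

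The test is also conservative: with 10% in both arms, its actual type I error is 0.9%. With 3/30 events on placebo, 11/30 on drug are needed for p ≤ 0.05 (p = 0.030). With 0/30 on placebo, 6/30 are needed (p = 0.024).

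**What an interval would add.** With Wilson limits (l, u) for each arm, the Newcombe 95% limits for d = p1 − p0 are d − √[(p1 − l1)² + (u0 − p0)²] and d + √[(u1 − p1)² + (p0 − l0)²].
- 9/30 vs 3/30: Fisher p = 0.104; excess 20 points, 95% CI −0.5 to 39.0.
- 10/30 vs 3/30: Fisher p = 0.057; excess 23.3 points, 95% CI 2.3 to 42.4.
- 0/30 on drug: one-sided 95% upper bound 1 − 0.05^(1/30) = 9.5%.

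In the first case test and interval agree that zero is not excluded, but only the interval shows that an excess of up to 39 points is also not excluded.

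**Does the interval detect more?** By the same enumeration, at 10% vs 30% the Newcombe interval includes zero in 51% of trials, and at 10% vs 20% in 84%. The uncertainty is still there; it is now reported.

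**The case against.** The strongest reply is that a 60-patient trial sized for a cognitive endpoint will have little power for adverse events under any method. That stands. The Newcombe interval would itself include zero in about half of trials at 10% vs 30%, so the 63% cannot be charged to the choice of Fisher's test alone.

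A reader might infer that the plan treats a non-significant test as proof of safety. It does not: no section defines a favourable safety result, a pass rule or a safety claim, and safety is not among the eight objectives in section 2.1. A reader might also infer that p-values are the only way safety is judged. That is too broad, because severity and causality are assessed for every event, events are followed up, and serious events are reported on expedited timelines (sections 9.1.11 and 11.4 to 11.7).

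Three further cautions hold:
- The rates and the sidedness are assumptions.
- No single pair of rates marks where power becomes adequate. Two-sided power reaches 80% near 44% on drug if placebo is 10%, near 36% if placebo is 5%, and near 25 to 26% if placebo is 0%.
- The 10/30 vs 3/30 contrast, where the test is non-significant but the interval excludes zero, arises partly because an exact test is more conservative than a Newcombe interval. It should not carry the argument.

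It may be said that counts per arm will be tabulated anyway. Nothing forbids it, but the plan does not commit to it, and counts alone are not an interval.

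**Conclusion.** The point holds in a limited form. The plan specifies a test for the between-arm comparison of adverse events and no estimate of its size. With 30 per arm, a two-sided test and assumed rates of 10% vs 30%, that test is non-significant in 63% of trials. The range is 51% if one-sided at 0.05, 29% for a larger excess (10% vs 40%) and 90% for a smaller one (10% vs 20%). The shortfall in detection comes mainly from sample size. The shortfall in the plan is that nothing in the specified output would show it. The efficacy analysis, the data collected and case-level safety actions are unaffected, so this is an inexpensive improvement in reporting and not a flaw in the trial's design.

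**What to change.** In section 3.0, Safety Assessments, make estimation the basis of the adverse-event comparison:
- For any AE, any SAE, AEs leading to discontinuation and each event type, report the number and percentage of patients per arm and the risk difference with a 95% confidence interval.
- Name one interval method in advance (for example Newcombe), so that the message cannot depend on a later choice.
- For events not seen on drug, report the one-sided 95% upper bound (9.5% for 0/30).
- Keep Fisher p-values as descriptive flags and state their sidedness.
- State that a non-significant difference will not be taken as evidence of safety.

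The cost is a few lines of SAP text and a revised table shell; no new data, visits or patients are needed. The drawback is that the intervals will be wide, so safety statements will be less reassuring.

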## 6.0 STUDY PROCEDURES

Study visits will include screening and 5 treatment visits (baseline, Weeks 1, 3, 6, and 9). Patients will be contacted by telephone at Weeks 2, 4, 5, 7, and 8 for monitoring of medication compliance, change in concomitant medication, and adverse events. Please see Appendix 1 – Schedule of Assessments.

At screening, the Structured Clinical Interview for Diagnosis for DSM Disorders (SCID) will be completed for confirmation of psychiatric diagnosis. A medical/psychiatric history will also be collected and a physical exam will be performed. Vital signs including weight, height, waist and hip measurement will be obtained at screening to record body mass index.

Subjects will be administered MMFS-202-302 at a fixed single dose of 2 grams (1 gram twice per day),

or placebo after the completion of the baseline assessments.

Methods:

- A) Measurement and Treatment Research to Improve Cognition in Schizophrenia (MATRICS) battery, including some supplemental cognitive assessments (FAS, ACT, WCST)
- B) Positive and Negative Syndrome Scale (PANSS) for schizophrenia and schizoaffective disorder
- C) MRI assessments:
  - a. Structure: MPRAGE (T1), T2
  - b. Function: Resting connectivity
  - c. Function: Reward/aversion and attention: fMRI paradigm of IAPS (standardized images selected to be neutral, pleasurable, or arousing) and Spinner Task
  - d. Function: Capacity working memory task
- D) A set of cognitive psychological paradigms performed outside of the magnet following the MRI scan:
  - a. Keypress task for an adaptation of the International Affective Picture Set (IAPS)
  - b. A spinner wheel rating task of the reward/aversion associated with monetary gains/losses
- E) Brief Negative Symptom Scale (BNSS)
- F) Calgary Depression Scale for Schizophrenia
- G) Clinical Global Impression of Severity (CGI-S) and Change (CGI-C)
- H) Measurement of RBC Mg at baseline and end of study
- I) EEG evaluation, measuring connectivity and activation using learning and memory tests

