## 8.0 STATISTICAL CONSIDERATIONS

### 8.1 Analysis of Clinical Data

Data will first be analyzed for efficacy on a per-protocol basis. The per-protocol population will include all subjects who complete all scheduled visits (+/- 5 days from planned visit time), have no protocol deviations that in the judgment of the principal investigator would invalidate their efficacy data, and achieve medication compliance of 80-120% (determined by pill counting; if pill packs are not available for confirmation, self-report of compliance will be used). Participants whose assessment falls +10 days or less from the scheduled visit will be included in per-protocol population, only if they were taking the study compound throughout. Data will secondarily be analyzed for efficacy on an intent-to-treat basis, with last observation carried forward (LOCF) for missing values or dropouts; subjects who did not receive any study compound will be excluded from the full analysis set, preserving the intent-to-treat principle. The primary analysis will be a univariate ANCOVA adjusting for baseline differences in the dependent measures of interest. We would also examine some variables categorically. The MATRICS working memory subscale T-score at 9 weeks will be the primary endpoint. Secondary endpoints will include the Clinical Global Impression of Change (CGI-C); the MCCB composite score; other individual cognitive domain subscale T-scores of the MCCB; a working memory composite score comprised of the 2 MCCB working memory subscale tests and the ACT test; and the PANSS positive and negative scales and BNSS. All endpoints will be evaluated as 9-weeks change from baseline, except for PANSS, which will be evaluated at both 6 and 9 weeks compared to baseline. Responder analyses will also be carried out using a chi-square test for the MCCB working memory subscale as a secondary endpoint evaluating clinical significance, using a cutoff of 0.5 standard deviation improvement (T-score improvement of  $\geq$  5 points). Finally, separate exploratory subgroup analyses will be performed on the MCCB working memory subscale T-score restricted to the subset of subjects who score 0, 0.5, or 1.0 SD or below the mean for normal age-matched normative data for that subscale. Analogous subgroup analyses will also be performed for the MCCB composite score, and the other MCCB subscale scores.

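### The safety population requires a staff encounter after dosing, so a dosed patient never seen again, whose death or other event is learned indirectly, drops out of the between-arm safety comparison

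*Combined protocol and SAP*

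**What the plan says.** Section 3.0, under Safety Assessments, sets two conditions that must both be met, exposure and later contact. The safety population consists of subjects "who had at least one exposure to a study compound, and who had any subsequent encounter with the study staff". This is the population for the safety analysis: "Safety will be evaluated with Fisher's exact tests, by comparing the following assessments between the MMFS-202-302 and Placebo groups". The items compared are adverse events, laboratory results, vital signs, weight and subjective remarks. The plan does not define an encounter, and it does not say how an event learned from a relative, clinic or hospital is counted when the patient had none.

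Section 8.1 defines the efficacy full analysis set without any such condition: "subjects who did not receive any study compound will be excluded from the full analysis set". Missing values there are carried forward.

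Section 6.0 starts study treatment after the baseline assessments and schedules later visits at Weeks 1, 3, 6 and 9. It adds calls: "Patients will be contacted by telephone at Weeks 2, 4, 5, 7, and 8". On size, Section 5.1 states: "We propose to study a total of 60 randomized participants, 30 receiving MMFS-202-302 and 30 randomized to placebo".

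Two other duties run alongside. Section 9.1.11 requires all observed or volunteered adverse events to be recorded. Section 11.7 requires notification of serious adverse events, whatever their attribution, during the study or within 30 days of the last dose. Neither section alters the analysis population set in Section 3.0.

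**The concern.** Whether a patient has an encounter after dosing is known only after treatment has begun, and treatment can influence it. Death or incapacity can be the very reason no encounter took place. A safety set defined this way can therefore exclude a patient because of the event that the comparison is meant to detect.

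The exposed interval runs from the first dose to the first later contact, planned for Week 1. Section 11.0 places the common side effects in the first week, and Section 13.0 lists rare but grave effects of very large amounts of magnesium, including cardiac arrest and death. With 30 patients per arm, a single death missing from the safety table would matter to anyone reading it.

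The two analysis sets also do not fit together. A dosed patient with no later contact belongs to the efficacy full analysis set but not to the safety set, although one would normally expect the safety set to be at least as inclusive among dosed patients.

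**Working it through.** The plan gives no figure for the safety population and no expected number of dosed patients without later contact, so there is no stated value to reproduce. The numbers of affected patients below are assumptions, used only to show size.

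**Who is dropped.** Section 6.0 plans 4 visits after baseline and 5 calls, so 4 + 5 = 9 scheduled contacts after the first dose. A patient leaves the safety set only with no encounter at all.

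- Dosed, any later visit: in the safety set; in the full analysis set.
- Dosed, reached later only by telephone: in the safety set if a call is an encounter, which the text leaves open; in the full analysis set.
- Dosed, never encountered again, event learned from a third party: out of the safety set, so both the event and the patient are missing from the comparison; in the full analysis set.
- Dosed, never encountered again, nothing known: out of the safety set, so only the denominator changes; in the full analysis set.

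**Effect on a rate.** Inputs: n = 30 dosed per arm (Section 5.1, assuming all randomized patients are dosed); k = 1 to 3 deaths in one arm without later contact (assumed); none in the other arm. Among all dosed the rate is k/30; under the written rule it is 0/(30 − k). Intervals are Clopper-Pearson 95%; p is the two-sided Fisher test of k/30 against 0/30.

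- k = 1: 1/30 = 3.3% (0.1 to 17.2%), p = 1.00; written rule 0/29 = 0% (0 to 11.9%).
- k = 2: 2/30 = 6.7% (0.8 to 22.1%), p = 0.49; written rule 0/28 = 0% (0 to 12.3%).
- k = 3: 3/30 = 10.0% (2.1 to 26.5%), p = 0.24; written rule 0/27 = 0% (0 to 12.8%).

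None of these comparisons would be significant at 0.05 even with every dosed patient included. What is lost is the death in the table, not a test result.

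**Effect on a commoner event.** Take 6/30 against 0/30: Fisher p = 0.024. If two of the six patients with the event are dropped, 4/28 against 0/30 gives p = 0.048. With 3 to 8 events against none, dropping one or two affected patients never moved p across 0.05.

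**Effect of including patients about whom nothing is known.** One event among 29 patients with follow-up is 1/29 = 3.4%. Adding one dosed patient with no information gives 1/30 = 3.3%. The wider definition counts that patient as event-free and lowers the rate slightly.

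**The case against.** The strongest reply is that the condition is very easy to meet. It asks for any later encounter, not attendance at Week 1, and nine contacts are scheduled. A patient admitted elsewhere in the first week and seen at a later visit stays in, and first-week effects reported at any later contact are counted. A reader might infer that the rule removes early events as a class. The wording does not support that: it selects on contact, not on when an event occurred.

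A reader might also infer that an early death would disappear from the trial record. It would not. Once staff know of it, Section 11.7 requires it to be notified as a serious adverse event. What is missing is its place in the between-arm comparison.

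Third, laboratory results, vital signs, weight and remarks all need contact after dosing, so for those items the clause costs nothing. Exposure may also be hard to confirm without a later contact, because adherence is checked by pill count or self-report at later visits (Sections 8.1 and 9.1.13) and Section 6.0 does not say whether the first dose is witnessed.

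Most of this stands, and it limits the point. It does not remove it: nothing in the plan restores a dosed patient with no later encounter. Doubt about exposure is already handled by the first condition, which requires exposure in its own right.

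**Conclusion.** The point holds in a narrow form and is minor. It applies to a dosed patient whom staff never encounter again and whose death or other event is learned indirectly. For that patient, one event and one member of the denominator are absent from the safety comparison, for example 0/29 in place of 1/30, while the efficacy full analysis set keeps the patient. Where nothing is known about a lost patient, only the denominator changes.

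Few patients are likely to be involved. The sizes shown rest on 30 dosed per arm and an assumed 1 to 3 such deaths, since the plan gives no number. The result also depends on what counts as an encounter: if telephone calls count, the group is smaller still.

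A reader might conclude that the clause serves no purpose and that deleting it has no drawback. That goes too far, because patients without follow-up then count as event-free and slightly dilute the rates. The case for change is that selection on an outcome of treatment is replaced by a small, visible dilution.

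**What to change.** In Section 3.0, define the safety population as all subjects with at least one exposure to study compound, and delete the condition on a later encounter. State that adverse events and deaths count whatever the source from which staff learn of them. Analyse laboratory results, vital signs and weight among subjects with post-dose values. List, by arm, the dosed subjects with no post-dose contact, so that a reader can see how many are counted as event-free for want of information.

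The cost is a few sentences and one short listing. No new data collection is needed, and no sample-size or power figure changes. The remaining drawback is the slight dilution shown above (3.4% to 3.3% for one event and one patient without follow-up).
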